3.2 Exclusion Criteria

3.2.1 Patients with known MSI-H / dMMR adenosquamous pancreatic or ampullary cancer

- 3.2.2 Patient has a known history or evidence of active brain/CNS metastases. Patients with treated brain/CNS metastases by surgery or radiation who are not on steroid therapy for this indication and have a stable MRI brain for 3 months are eligible for the study.
- 3.2.3 Patient who has had chemotherapy, radiation, or biological cancer therapy within 14 days prior to the first dose of study drug. With the following caveats: 28 days for pelvic radiotherapy, 6 months for thoracic region radiotherapy that is > 30 Gy. Hormonal therapy in the setting of a second, hormone-sensitive malignancy not thought to have impact on longevity (i.e. prostate cancer, early stage breast cancer) are allowed at the discretion of the principal investigator.
- 3.2.4 Patient has received an antineoplastic investigational agent or used an investigational device within 28 days of the first dose of study drug.
- 3.2.5 Patient is expected to require any other form of systemic or localized antineoplastic therapy while on study. Exceptions are hormonal therapy in the setting of a second, hormone-sensitive malignancy not thought to have impact on longevity (i.e. prostate cancer, early stage breast cancer)
- 3.2.6 Patients who have had major surgery within 28 days of dosing of investigational agent, excluding minor procedures (dental work, skin biopsy, port placement, etc.), celiac plexus block, biliary stent placement, etc.
- 3.2.7 Patients who have received a live vaccine within 28 days prior to the first dose of study drug. Seasonal influenza vaccines for injection are generally killed virus and are allowed; however, intranasal influenza vaccines (e.g. FluMist®) are live attenuated vaccines and are not allowed.
- 3.2.8 Patients with a history of prior treatment with immune checkpoint inhibitor therapy including anti-PD-1, anti-PD-L1, anti-PD-L2, anti-CTLA4, anti-OX40, and anti-LAG-3 antibodies.
- 3.2.9 Have used any systemic steroids within 14 days of study treatment.
- 3.2.10 History of severe hypersensitivity reaction to any monoclonal antibody.
- 3.2.11 Evidence of clinically significant ascites, defined as requiring a paracentesis within the last 3 weeks OR clinical symptoms with palpable ascites on exam
- 3.2.12 Have clinically significant and/or malignant pleural effusion (pleural effusions that are not clinically significant are allowed, defined as no more than 25% fluid level of the corresponding hemithorax and stable fluid level [non-progressive] over at least 6 weeks documented radiographically).
- 3.2.13 Uncontrolled intercurrent illness including, but not limited to, ongoing or active infection, symptomatic congestive heart failure, unstable angina pectoris, cardiac

- arrhythmia, or psychiatric illness/social situations that would limit compliance with study requirements.
- 3.2.14 History of autoimmune disease requiring systemic immunosuppression within the last 2 years.
- 3.2.15 Presence of any tissue or organ allograft, regardless of need for immunosuppression, including corneal allograft. Patients with a history of allogeneic hematopoietic stem cell transplant will be excluded.
- 3.2.16 All toxicities attributed to prior anti-cancer therapy other than alopecia and fatigue must have resolved to grade 1 (National Cancer Institute Common Terminology Criteria for Adverse Events [CTCAE], version 5.0) or baseline before administration of study drug. Subjects with toxicities attributed to prior anti-cancer therapy which are not expected to resolve and result in long-lasting sequelae, such as neuropathy after chemotherapy, are permitted to enroll.
- 3.2.17 Known active HAV, HBV, or HCV infection, as defined by elevated transaminases with the following serology: positivity for HAV IgM antibody, anti-HCV, anti-HBc IgG or IgM, or HBsAg (in the absence of serology suggesting prior immunization or achieve immunity). Patients who are hepatitis C antibody positive may be enrolled if they are confirmed with negative viral load at screening.
- 3.2.18 Patient has a pulse oximetry of \leq 92% on room air.
- 3.2.19 Patient is on supplemental home oxygen.
- 3.2.20 Patient has an unhealed surgical wound or ulcer, or a bone fracture considered non-healing.
- 3.2.21 Patient has clinically significant heart disease (such as uncontrolled angina, myocardial infarction within the last 3 months or congestive heart failure of New York Heart Association III or IV).
- 3.2.22 Patient is, at the time of signing informed consent, a regular user (including "recreational use") of any illicit drugs or other substance abuse (including alcohol) that could potentially interfere with adherence to study procedures or requirements.
- 3.2.23 Patient is unwilling or unable to follow the study schedule for any reason.
- 3.2.24 Patient has history of non-infectious pneumonitis.

3.3 Inclusion of Women and Minorities

Both men and women of all races and ethnic groups are eligible for this trial.

4. REGISTRATION

4.1 General Guidelines

Eligible patients will be entered on study at the Sidney Kimmel Comprehensive Cancer Center at the Johns Hopkins University by the Lead Study Coordinator. All sites should contact the Lead Study Coordinator to verify ongoing study enrollment.

If a patient does not receive protocol therapy following registration, the patient's registration on the study may be canceled. The Study Coordinator should be notified of cancellations as soon as possible.

4.2 Registration Process

To register a patient, the following de-identified documents should be completed and sent to the Lead Study Coordinator

- Registration Form
- Signed patient consent form
- Eligibility Checklist
- Copy of required screening tests and scans

To complete the registration process, the Lead Study Coordinator will:

- Assign a patient study number
- Register the patient on the study

5. TREATMENT PLAN

5.1 Retifanlimab Administration

Treatment will be administered on an outpatient basis. Dosing delays are described in **Section 6.2**. No investigational or commercial agents or therapies other than retifanlimab may be administered with the intent to treat the subject's malignancy.

SUMMARY DESCRIPTION				
Agent	Premedications; Precautions	Dose	Route	Cycle Length
Retifanlimab	No prophylactic pre-medication will be given unless indicated by previous experience in an individual subject per Section 5.2 .	500 mg	IV infusion over 30 minutes*	28 days

^{*}Infusion times are approximate (-5/ +15 min) and may need to be adjusted based on subject tolerability.

5.2 General Concomitant Medication and Supportive Care Guidelines

Retifanlimab is a fully human monoclonal immunoglobulin (Ig) G44 κ antibody. Subjects should be closely monitored for potential AEs during antibody infusion and potential AEs throughout the study.

5.2.1 Infusion Reactions

Infusion or hypersensitivity reactions may be observed with administration of any foreign protein. Premedication with acetaminophen/paracetamol and a histamine blocker should be considered for participants who have had previous systemic reactions to protein product infusions or when recommended by institutional policy.

Guidelines for management of suspected infusion reactions are provided in Table 1.

Table 1: Guidelines for Management of Suspected Infusion Reactions

Grade	Description ^{a)}	Treatment	Subsequent Infusions
1	Mild reaction; infusion interruption not indicated; intervention not indicated.	Monitor vital signs closely until medically stable.	Premedication with acetaminophen/paracetamol and a histamine blocker should be considered for participants who have had previous systemic reactions to protein product infusions or when recommended by institutional policy.
2	Requires infusion interruption but responds promptly to symptomatic treatment (e.g., antihistamines, NSAIDS, narcotics, IV fluids); prophylactic medications indicated for ≤ 24 hours.	First occurrence: Stop infusion and initiate appropriate medical measures (e.g., IV fluids, antihistamines NSAIDS, acetaminophen/paracetamol, narcotics, per institutional preferences). Monitor vital signs until medically stable. If symptoms resolve within 1 hour, infusion may be resumed at 50% of the original infusion rate. Subsequent occurrences (after recommended prophylaxis): Permanently discontinue study treatment.	Premedicate at least 30 minutes before infusion with antihistamines (e.g., diphenhydramine 50 mg PO) and acetaminophen/paracetamol (500-1000 mg PO). Additional supportive measures may be acceptable (per institutional preference) but should be discussed with medical monitor. Next infusion should start at 50% of the original infusion rate. If no reaction, rate of infusion can be increase by 25% every 15 minutes until a rate of 100% has been reached. Subsequent infusions can begin at 100%.
3 or 4	Grade 3: Prolonged (i.e., not rapidly responsive to symptomatic medication and/or brief interruption of infusion); recurrence of symptoms following initial improvement; hospitalization indicated for other clinical sequelae (e.g., renal impairment, pulmonary infiltrates). Grade 4: Life-threatening; pressor or ventilatory support indicated.	Stop infusion and initiate appropriate medical therapy (e.g., IV fluids, antihistamines NSAIDS, acetaminophen/paracetamol, narcotics, oxygen, pressors, epinephrine, corticosteroids, per institutional preferences). Monitor vital signs frequently until medically stable. Hospitalization may be indicated.	Permanently discontinue study treatment.

a) Per NCI CTCAE v5.0, appropriate resuscitation equipment should be available at the bedside and a physician readily available during the period of study treatment administration.

Please refer to **Section 6.2** for guidelines to manage treatment delays due to retifanlimab infusion-related reactions.

5.2.2 Retifanlimab Related Adverse Events

Blocking PD-1 function may permit the emergence of auto-reactive T cells and resultant clinical autoimmunity. Rash/pruritus, diarrhea/colitis, pneumonitis, hepatitis, and hypothyroidism were drug-related, presumptive autoimmune events noted in previous anti-PD1 studies.

For the purposes of this study, a retifanlimab-related AE is defined as an AE of unknown etiology, associated with drug exposure and is consistent with an immune phenomenon. Efforts should be made to rule out neoplastic, infectious, metabolic, toxin or other etiologic causes. Serological, immunological, and histological (biopsy) data should be used to support the diagnosis of an immune-mediated toxicity. Suspected retifanlimab-related AEs must be documented on an AE or SAE CRF. Identification and treatment of retifanlimab-related AEs can be found in NCCN's guidelines for the management of immunotherapy-related toxicities. Additional guidance can be found in the Retifanlimab Investigator's Brochures (IB).

5.3 Prohibited and/or Restricted Medications and Devices

The following therapies or devices are not permitted during the treatment period (if administered, the subject may be removed from the study):

- Immunosuppressive agents unless they are utilized to treat an AE or as specified in **Sections 5.2** and **5.6**.
- Any non-study anticancer chemotherapy or immunotherapy (approved or investigational) with the exception of subjects in the survival period of the study, with the exception of hormonal therapy in the setting of a second, hormone-sensitive malignancy not thought to have impact on longevity (i.e. prostate cancer, early stage breast cancer)
- Any major surgery or surgical procedure; if required must be discussed with the IND Sponsor to determine if it is appropriate for the subject to continue study treatment
- Another investigational agent
- Live vaccines (examples of live vaccines include, but are not limited to: measles, mumps, rubella, chicken pox, yellow fever, rabies, BCG, and typhoid [oral] vaccine). Seasonal influenza vaccines for injection are generally killed virus vaccines and are allowed. However, intranasal influenza vaccines (e.g. Flu-Mist®) are live attenuated vaccines, and are not allowed.
- Palliative (limited-field) radiation therapy is permitted, but only for pain control and with approval by the IND Sponsor.
- Systemically active steroids can be used but should be reported to the IND Sponsor. Steroid treatment should be completed at least 14 days prior to resuming study-related treatments. Patients requiring adrenal replacement steroid doses ≤ 10 mg daily prednisone equivalent (in the absence of active autoimmune disease) may resume treatment if approved by the IND Sponsor.
- Use of growth factors unless prior discussion and agreement with the IND Sponsor.
- Use of allergen hyposensitization therapy

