Complete unacceptable toxicity criteria can be found in **Section 5.7**. At the investigator's discretion, subjects may receive additional cycles of treatment if they are clinically stable and meet dosing eligibility criteria. All subjects may continue in the treatment period until the criteria in **Section 5.9** are met. Subjects may continue on treatment with radiographic disease progression if clinically stable and investigator believes the treatment is providing benefit. Subjects will be considered in the treatment period until 28 days after the last dose of study drug.

Patients who have a confirmed complete response by two scans ≥ 4 weeks apart and who have been on retifanlimab treatment for at least 6 months may discontinue retifanlimab treatment at the discretion of the investigator after receiving at least two doses beyond the initial determination of CR. Patients with SD, PR or CR that received at least 24 months of retifanlimab may also discontinue retifanlimab at the discretion of the investigator. Retifanlimab may be resumed upon disease recurrence or progression in these patients. Criteria and procedures for retreatment are described in Sections 5.9.2 and 10.0.

After completion of treatment and end of treatment (EOT) visit assessments, all subjects, including those who did not receive treatment, will continue to be followed every three months (± 2 weeks) by telephone, e-mail, or optional clinic visit until death, withdrawal of consent, or closure of study. Subjects will also be contacted at 90 days (+14 day reporting window) from the last dose of therapy. Information on survival and new cancer therapies will be collected. All subjects who discontinue study treatment should continue to be monitored for disease status by radiologic imaging every two months (± 2 weeks) until: 1) the start of a new antineoplastic therapy (information of the new cancer therapy will be collected), 2) disease progression, 3) death, 4) withdrawal of consent, or 5) the close of the study, whichever occurs first. All subjects will be followed after their last dose of study drug for the development of adverse events (AEs) and serious adverse events (SAEs) as described in **Section 7.5**.

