5.7.2 Use in Pregnancy

The investigational agents used in this protocol may have adverse effects on a fetus; therefore, women with a positive pregnancy test at screening will not be eligible for enrollment. If a subject inadvertently becomes pregnant while on treatment, the subject will immediately be removed from the study. The site will contact the subject at least monthly and document the subject's status until the pregnancy has been completed or terminated

Pregnancy in female subjects or in partners of male subjects throughout the study or within 6 months of completing treatment should be reported initially as a serious adverse event (see reporting procedures in **Section 7.5.6**) by the investigator within 24 hours of learning of its occurrence. Pregnancy information must be reported on the Pregnancy Form.

Protocol required procedures for study discontinuation and follow-up must be performed on the subject unless contraindicated by pregnancy (e.g., x-ray studies). Other appropriate pregnancy follow-up procedures should be considered if indicated.

Follow-up information regarding the course of the pregnancy, including any voluntary or spontaneous termination, perinatal and neonatal outcome and where applicable, offspring information must be reported on the Pregnancy Follow-up Form. Pregnancy outcomes must also be collected for the female partners of any males in this trial. Consent to report information regarding these pregnancy outcomes should be obtained from the female partner.

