5.9 Criteria for Removal from Treatment

The reason for study removal and the date the subject was removed will be documented in the CRF.

A subject will be discontinued from the trial for any of the following reasons:

• The subject or legal representative (such as a parent or legal guardian) withdraws consent for participation in the study.

A subject must be discontinued from treatment (but may continue to be monitored in the post-treatment follow-up portion of the trial) for any of the following reasons:

- The subject or legal representative (such as a parent or legal guardian) withdraws consent for treatment.
- Intercurrent illness that prevents further administration of treatment,
- Unacceptable toxicity (see **Section 5.6**). Exceptions for treatment discontinuation are listed in **Section 5.6**,
- Disease progression as defined in **Section 5.9.1**,
- Severe or life-threatening retifanlimab-related AE(s) (see Section 6.2),
- Need for >2 dose delays due to the same drug-related toxicity as per the dose delay guidelines (see **Section 6.2**),
- If, in the opinion of the Investigator, a change or temporal or permanent discontinuation of therapy would be in the best interest of the subject.
- Noncompliance with trial treatment or procedure requirements,
- Subject is lost to follow-up, or
- Subject becomes pregnant.

A subject may, at the discretion of the Investigator, be discontinued from treatment (but may continue to be monitored in the post-treatment follow-up portion of the trial) if they have:

- Completed 6 months of treatment with retifanlimab and has a complete response (CR) by at least two scans ≥ 4 weeks apart AND have received at least two doses of retifanlimab beyond the initial determination of CR.
- Completed 24 months of treatment with retifanlimab and has a response of stable disease, partial response, or complete response at the time of discontinuation

Note: time on treatment is calculated from the date of first dose.

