11. STUDY ENDPOINTS

11.1 Primary Endpoint

The primary endpoint is DCR at 4 months following the start of treatment with retifanlimab, which is defined as the proportion of subjects with PR or CR or stable disease according to RECIST 1.1 following 4 months from the start of therapy. Subjects who discontinue due to toxicity prior to post-baseline tumor assessments will be evaluable and considered treatment failures. Otherwise, subjects who discontinue or do not have any post-baseline scans for other reasons including withdrawal of consent or being lost to follow-up prior to C2D1 will be replaced and not included in the primary efficacy analysis.

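### Sections 5.3 and 5.7.2 take patients out of the study where 5.9 and 1.4 keep them in follow-up, and 11.1 can then replace some unscanned patients in the primary DCR

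*Combined protocol and SAP*

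**What the plan says.** Section 5.3 introduces its list with the words "not permitted during the treatment period (if administered, the subject may be removed from the study". It attaches no rule for follow-up or analysis after removal. By section 1.4 the period concerned is long: "Subjects will be considered in the treatment period until 28 days after the last dose of study drug".

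Section 5.7.2 is firmer on pregnancy: "the subject will immediately be removed from the study". It nevertheless also asks for at least monthly contact and for the protocol's discontinuation and follow-up procedures.

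Section 5.9 has two lists. The first opens "A subject will be discontinued from the trial for any of the following reasons" and has one entry, withdrawal of consent for participation. The second opens "A subject must be discontinued from treatment (but may continue to be monitored in the post-treatment follow-up portion of the trial". It includes pregnancy and "Noncompliance with trial treatment or procedure requirements", but does not name prohibited therapy. Section 1.4 has all subjects contacted every three months "until death, withdrawal of consent, or closure of study".

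On the primary endpoint, section 11.1 counts patients who stop for toxicity before any scan as failures. Otherwise, "subjects who discontinue or do not have any post-baseline scans for other reasons" are replaced and left out of the primary analysis. Section 13.1 defines evaluability as one dose plus either a post-baseline assessment or an earlier stop for toxicity or clinical progression. Section 11.1 does not mention clinical progression.

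**The concern.** The protocol gives two answers to whether a patient can be taken off study without withdrawing consent. A site that follows 5.3 literally can end contact with a patient whom 1.4 says must be followed.

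Such removals are unlikely to be unrelated to outcome. A patient who needs surgery, immunosuppression or another anticancer drug is more likely than average to be doing badly. If that patient has not yet been scanned and the removal is recorded under its own reason, 11.1 hands the place to someone else and a probable failure leaves the denominator. With a success rule of 3 in 21, a small shift in who is counted matters. After removal, the date of death may also be lost and, for some listed items, later scans and the 90-day safety contact.

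**Working it through.** **1. What removal under 5.3 adds, endpoint by endpoint**

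- **OS.** Section 1.4 promises contact until death, and removal would end it. Section 13.2 then censors at the date last known alive. This loss comes directly from 5.3.
- **PFS, imaging and late safety after new anticancer therapy.** Imaging already stops at the new therapy (1.4, 5.12.2). PFS is already censored at the last scan before it (13.2). The safety contact already moves to within 7 days before it (5.12.1). Section 5.3 adds nothing here.
- **PFS, imaging and late safety after other listed items** (for example surgery, a live vaccine or a growth factor). No other section stops imaging or the 90-day contact for these, so a loss would come from 5.3.
- **DCR after a first scan.** Section 13.1 keeps the patient evaluable. How a missing 4-month assessment is then counted is not stated.
- **DCR before the first scan (about week 8).** A stop for toxicity stays in under 11.1 and 13.1. A stop for clinical progression stays in under 13.1 only. Any other recorded reason leads to replacement under 11.1. The words about C2D1 in 11.1 can be read as shortening this window.

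**2. The plan's own error rate**

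Inputs from 13.1: 7 patients in stage 1, stop at 0; 21 in total, reject at 3 or more; null DCR 5%.

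P(reject) = P(X1=1)·P(X2≥2) + P(X1=2)·P(X2≥1) + P(X1≥3), with X1 ~ Bin(7, p) and X2 ~ Bin(14, p).

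At p = 0.05: 0.2573 × 0.1530 + 0.0406 × 0.5123 + 0.0038 = 0.0394 + 0.0208 + 0.0038 = 0.064. This matches the plan. Power at 30% is 0.904 and the chance of early stopping at 5% is 0.698, which also match.

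**3. Effect of replacing unscanned failures**

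Assume that a share q of treated patients, all failures, is removed and replaced. The DCR among those counted becomes 0.05/(1 − q).

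| q (assumed) | DCR among counted | Type I error | Treated for 21 counted, 21/(1 − q) |
|---|---|---|---|
| 0 | 5.0% | 0.064 | 21 |
| 5% | 5.3% | 0.072 | 22.1 |
| 10% | 5.6% | 0.082 | 23.3 |
| 15% | 5.9% | 0.093 | 24.7 |

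The last column stays within the 25 planned.

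**4. Outer bound**

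At most 25 − 21 = 4 patients can be replaced. If k failures are replaced, the formula in step 2 applies with 21 + k patients, of whom 7 + k1 are in stage 1. Over the possible k1, type I error is 0.070–0.075 (k = 1), 0.075–0.086 (k = 2), 0.081–0.098 (k = 3) and 0.087–0.110 (k = 4). It reaches 0.10 only if all four spare places go to failures: 0.100 with two of them in stage 1, 0.105 with three, 0.110 with four.

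**5. Effect on the estimate**

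3/21 = 14.3%. With one excluded failure restored, 3/22 = 13.6%, a change of about 0.65 points. With four restored, 3/25 = 12.0%.

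**The case against.** The strongest reply is that 5.3 is optional and loosely worded. Section 5.9 is titled as removal from treatment, yet its first sentence speaks of study removal, so 5.3 may mean only that study drug stops. Its surgery and steroid items, which discuss continuing or resuming treatment, point the same way. This is a fair reading and it lowers the likely frequency. It does not settle the text, because 5.9 separates leaving the trial from stopping treatment and 5.3 uses the term for the former.

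Several stronger inferences are tempting, and the documents do not support them:

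- **That failing patients in general drop out of DCR, PFS and late safety.** Section 13.1 keeps those with a scan, toxicity or clinical progression. After new anticancer therapy, the PFS and safety cut-offs come from other sections and would remain after any change to 5.3.
- **That patients given steroids or palliative radiation fall under the removal clause.** The list itself allows both under conditions, and excepts immunosuppressants used to treat an adverse event.
- **That an early switch of therapy always lacks an exemption.** Section 5.12.3 ties the survival period to progression, but footnote 23 of the study calendar does not.
- **That 5.7.2 ends follow-up in pregnancy.** It still requires follow-up procedures, so the conflict is one of wording.
- **That each removed failure is worth 1/21 = 4.8 points.** That is the effect of turning a failure into a success. Leaving one failure out moves the estimate by about 0.65 points.

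On OS, 13.2 plans calls, certified mail and public-record checks for patients lost to follow-up, which may recover some deaths.

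**Conclusion.** The contradiction stands: 5.3 permits and 5.7.2 requires removal from the study, while 5.9 limits trial exit to withdrawal of consent and 1.4 follows everyone. The direct loss is in survival follow-up, which is exploratory, plus imaging and the 90-day contact for listed items other than new anticancer therapy.

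For the primary DCR the risk is confined to treated patients removed before the first post-baseline scan for a recorded reason other than toxicity or clinical progression. The omission of clinical progression from 11.1 is a separate mismatch with 13.1 that widens this gap if 11.1 is applied alone.

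The size is modest. Under assumed shares of 5% to 15%, type I error is 0.072 to 0.093, below the 0.10 target. Only the extreme use of all four spare places reaches or passes it. These figures assume that every removed patient is a failure and is replaced; the documents give no rate. The point is worth correcting because the correction is cheap, not because the design fails.

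**What to change.** - **Sections 5.3 and 5.7.2:** replace removal from the study with discontinuation from study treatment, with follow-up continuing under 1.4, 5.9 and the follow-up sections (5.12.1 to 5.12.3). Whether study drug stops is left as the protocol has it.
- **Section 11.1:** state that a treated patient stopped under 5.3 before the first post-baseline scan is counted as not having disease control and is not replaced.
- **Sections 11.1 and 13.1:** use the same rule for clinical progression before the first scan.

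The cost is a few sentences. A few more patients are followed under visits already in the calendar, and the reported DCR may be slightly lower. In return, the stated type I error of 0.064 is protected against this route of loss.
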